### **3.6.4.1. PRIMARY EFFICACY ENDPOINT**

Under the assumption of monotonicity, a trend test will be performed as primary efficacy analysis. For small deviations from monotonicity (comprised in standard variation on ACR20 response rate), the power of the trend test remains sufficiently high. For the descriptive statistics (frequency, percentage) and trend test on the primary efficacy endpoint, data will be analyzed according to the ITT principle; thus, subjects will be analyzed according to the treatment to which they were assigned. Subjects with missing ACR20 response at Week 12 will be treated as non-responders (non-responder imputation approach).

Additionally, each dose group will be tested separately against placebo using a Chi or Fisher exact test (or other test if deemed more relevant). The study is only powered for testing the trend of the primary endpoint. All other p-values are exploratory and no correction for multiple testing is foreseen.

If ACR20 cannot be calculated at Week 12, such subjects will be considered to not have achieved an ACR20 response.

Subjects who meet any of the following treatment failure criteria will be considered nonresponder for the primary endpoint analysis:

- Initiate treatment with DMARDs (other than MTX), systemic immunosuppressives, and/or biologics for RA prior to Week 12.
- Increase dose of MTX above the baseline dose for RA prior to Week 12.
- Initiate treatment with oral corticosteroids for RA, increase the dose of oral corticosteroids for RA above the baseline dose, or receive i.v. or i.m. administration of corticosteroids for RA prior to Week 12.
- Treatment with intra-articular corticosteroids between Week 8 and Week 12.

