##### **Study drug must also be permanently discontinued if any of the following occurs:**

- Serious hypersensitivity reaction.
- Following abnormalities in laboratory test results: ALT and/or AST elevations between > 3 and  $\leq$  5 x ULN (confirmed by repeat testing on 2 consecutive visits),

ALT or AST elevations  $> 5 \times$  ULN, absolute neutrophil count  $< 1 \times 10^9/L$ , or a platelet count  $< 50 \times 10^3/\mu L$ .

- Diagnosis of or suspicion of a serious infection (requiring parenteral antibiotic and/or hospitalization) or TB.
- Malignancy.
- Pregnancy or pregnancy planned within the study period.
- Demyelinating disease.
- The initiation of protocol-prohibited medications (see section [3.3.6](#)).
- Congestive heart failure (CHF) class III or IV as defined by the New York Heart Association, unstable angina pectoris, myocardial infarction, cerebrovascular accident.
- In case of interruption of study drug administration for 2 consecutive doses.
- The randomization code is broken prematurely by the Investigator or his/her staff.
- The Investigator or the Sponsor's medical monitor deems it is in the subject's best interest.

Discontinuation of study drug must be considered for subjects who develop a severe study drug injection-site reaction or a severe hypersensitivity reaction.

Subjects who have to discontinue according to these criteria but are not withdrawing consent for post-treatment follow-up should return for the Early Termination Visit planned 2 weeks after the last study drug administration (unless they discontinue during a study visit, in which case that becomes their Early Termination Visit). Subjects should also have a Follow-up Visit planned 12 weeks after the last study drug administration, according to section [3.4.1.3](#).

A description of assessments to be performed for subjects who discontinue from the study is provided in section [3.4.1.3](#) (also see Early Termination Visit in the [Schedule of Assessments](#)).

For all subjects, every effort should be made to contact the medical monitor prior to discontinuing study drug, where medically feasible. If there is a medical reason for discontinuation, the subject will remain under the supervision of the Investigator until satisfactory health has returned unless the subject withdraws his consent and is no longer willing to come to the visits. Subjects who discontinue will not be replaced.

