#### Permitted Medication

Stable dose and route of MTX (12.5-25 mg weekly) maintained during the 6 consecutive weeks prior to screening and for the duration of the study. The concomitant medication dose may be reduced or temporarily discontinued because of abnormal laboratory values, side effects, concurrent illness, or the performance of a surgical procedure, but the change and reason for the medication should be clearly documented in the subject's medical record and in the (e)CRF.

Subjects treated with NSAIDs (including aspirin and selective cyclooxygenase 2 inhibitors) and other analgesics (except high-potency opioid analgesics, such as World Health Organization [WHO] class IV drugs [e.g., morphine; see prohibited

medication]) should receive the usual marketed doses approved in the country in which the study is being conducted and should be on a stable dose from at least 2 weeks prior to screening until the Week 24 Visit, or until the Early Termination Visit. Changes in the dose may be done at the discretion of the Investigator if the subject develops unacceptable side effects. Whenever possible, short-acting NSAIDs and other analgesics should not be administered within 6 hours before study assessments. Long-acting ones can be maintained at their usual dosing intervals before study assessments.

Subjects treated with oral corticosteroids should receive a stable dose equivalent to  $\leq 10$  mg of prednisone/day, for at least 2 consecutive weeks prior to screening, and continue this dose up to and including Week 24, or until the Early Termination Visit. The dose of oral corticosteroid may be decreased at the discretion of the Investigator only if the subject develops unacceptable side effects.

The number of intra-articular corticosteroid injections is limited to 2 injections over a 24-week period. Intra-articular injections may not be given from Week 8 until Week 12. The joint(s) affected by the procedure(s) will be considered as swollen and tender for 28 days/4 weeks in the data analyses from the date of the procedure onward.

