## Prohibited Medication

The following medications are prohibited during the study (up to and including Week 24 or Early Termination Visit):

- DMARDs other than a stable background dose of MTX.
- i.m or i.v. administration of corticosteroids for the treatment of RA. Any increase in oral corticosteroids above the baseline. For intra-articular dosing see "permitted medication".
- High-potency opioid analgesics, including but not limited to hydrocodone, metopon, oxycodone, clonitazene, hydromorphone, oxymorphone, morphine, fentanyl, levorphanol, buprenorphine, methadone, meperidine.
- Use of any biologic DMARD, targeted synthetic DMARD (such as tofacitinib), or investigational drugs.
- Use of any live attenuated vaccine.

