### 3.6.4. EVALUATION OF EFFICACY PARAMETERS

The primary endpoint is the reduction of signs and symptoms of RA evaluated by calculating the proportion of subjects achieving an ACR20 response at Week 12.

The following efficacy analyses will be performed in addition to the primary analysis:

- The proportion of subjects achieving an ACR response of 20, 50, and 70 over time will be summarized by treatment group.
- ACR-N index of improvement over time will be summarized by treatment group.
- The DAS28 (using CRP and ESR) score over time will be summarized by treatment group.
- The proportion of subjects with EULAR response over time will be summarized by treatment group.
- The change from baseline (absolute change) in disease activity over time will be summarized by treatment group. The following disease activity scores will be used:
  - DAS28 (CRP and ESR)
  - SDAI
  - CDAI
- The proportion of subjects in remission over time will be summarized by treatment group and compared between the groups. The proportion of subjects who maintained in remission at consecutive time points; i.e., at Weeks 12, 16, 20, 24 will be summarized by treatment group.

The following disease remission definitions will be used:

- DAS28 (ESR) < 2.6
- SDAI  $\leq$  3.3
- CDAI  $\leq$  2.8
- Boolean: TJC  $\leq$  1, SJC  $\leq$  1, CRP  $\leq$  1 mg/dL, VASPA  $\leq$  1 (on a 0-10 scale)
- The change from baseline (absolute change) in HAQ-DI over time will be summarized by treatment group.
- The proportion of HAQ-DI responders (i.e., those who have a clinically meaningful improvement from baseline of  $\geq$  0.25 [absolute change] in HAQ-DI) over time will be summarized by treatment group.
- The proportion of subjects with HAQ-DI  $\leq$  0.5, defining normal physical function, over time will be summarized by treatment group.
- The proportion of subjects with HAQ-DI  $\leq$  0.5 (normal physical function) with or without remission (DAS28, SDAI, CDAI, and Boolean) at Week 24 will be summarized by treatment group.

- The changes from baseline (absolute change) in the physical and mental component scores of the SF-36 at Week 12 and at Week 24 will be summarized by treatment group.
- The change from baseline (absolute change) in SF-36 scales at Week 12 and at Week 24 will be summarized by treatment group.
- The change from baseline (absolute change) in FACIT-Fatigue at Week 12 and at Week 24 will be summarized by treatment group.

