- The duration of morning stiffness at Week 24 will be summarized by treatment group.

Primary and secondary efficacy endpoints will be analyzed according to the ITT principle. Summary statistics for continuous efficacy endpoints include mean (and associated 95% confidence interval), standard deviation, median, minimum and maximum. For categorical efficacy endpoints frequency and proportion or percentage (together with 95% confidence interval) will be calculated. Analysis on the primary endpoint will be repeated for the PP population, as a sensitivity analysis.

Subgroup analyses will be performed to evaluate consistency of the primary and secondary efficacy endpoints over covariates including demographics (including weight and region), baseline disease characteristics (including disease duration, RF category and anti-CCP category), baseline and prior medications, and site.

Unless specified otherwise, non-responder imputation for missing binary efficacy endpoints will be applied, whereas missing continuous efficacy endpoints will be imputed by last observation carried forward.

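### The treatment-failure rule covers only the primary Week 12 ACR20, so a subject who fails there can still count as a responder in the secondary tables

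*Combined protocol and SAP*

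**What the plan says.** **The rule.** Section 3.6.4.1 says that subjects who meet any listed treatment-failure criterion "will be considered nonresponder for the primary endpoint analysis". Four criteria follow. Three concern events before Week 12: starting another DMARD, an immunosuppressive or a biologic; raising MTX above baseline; and starting or raising oral corticosteroids or receiving them i.v. or i.m. The fourth is "Treatment with intra-articular corticosteroids between Week 8 and Week 12".

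**The secondary endpoints.** Section 3.6.4: "The proportion of subjects achieving an ACR response of 20, 50, and 70 over time will be summarized by treatment group". EULAR response, remission and HAQ-DI response are also reported over time. Section 3.6.4.2 adds only summary statistics. The general imputation rule in Section 3.6.4 sets missing binary outcomes to non-response, while "missing continuous efficacy endpoints will be imputed by last observation carried forward". Absent data trigger this rule; medication does not.

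**Provisions that limit the consequence.**
- Section 3.2.3.2: starting prohibited medication requires permanent discontinuation of study drug. The subject "should return for the Early Termination Visit planned 2 weeks after the last study drug administration", unless the discontinuation happens at a study visit.
- Section 3.3.6: the prohibited list runs to Week 24 or Early Termination. Intra-articular corticosteroid is dealt with under permitted medication, with at most two injections in 24 weeks, and "Intra-articular injections may not be given from Week 8 until Week 12".
- Sections 3.3.6 and 3.4.2.1: an injected joint is scored swollen and tender for 28 days, and this is not confined to the primary endpoint.

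**The concern.** ACR20, ACR50 and ACR70 are nested: anyone who meets ACR50 meets ACR20. A failure rule attached to one level at one visit breaks the nesting. Read literally, the Week 12 results could show the same subject failing ACR20 in the primary analysis and achieving ACR20 or ACR50 in the over-time summary. After Week 12 no failure criterion exists, so an observed response under newly started medication counts as response to the assigned arm.

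The primary test is not at stake. The supporting evidence is: Section 3.1.1 relies on ACR50, ACR70 and remission to support efficacy, Section 3.6.4 compares remission between groups, and the secondary objective in Section 2 includes choosing the dose regimen.

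**Working it through.** **1. Routes by which a failure event and an observed assessment can coexist**

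- *Intra-articular injection in Weeks 8 to 12.* It is a failure criterion in 3.6.4.1. Section 3.3.6 bars it but places it under permitted medication, so it is not clear that the discontinuation trigger in 3.2.3.2 applies. The subject may stay and be assessed at Week 12.
- *Medication started shortly before an Early Termination Visit.* Dosing is two-weekly and that visit is two weeks after the last dose. A subject last dosed at Week 10 is due at Week 12; last dosed at Week 14 or 18, at Week 16 or 20. The Schedule of Assessments includes joint counts, pain, global assessments and HAQ-DI at Early Termination. If the value is analysed at that scheduled week, nothing is missing and non-responder imputation does not apply. The documents do not say how these values are assigned to analysis visits.
- *Medication started after the Week 22 dose.* No study dose remains to be stopped, and Week 24 is the next efficacy assessment. The response is observed and no failure criterion applies.

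**2. What the limiting provisions do and do not cover**

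- Discontinuation makes binary outcomes after Early Termination missing, hence non-response. It does not affect the assessment made at that visit.
- The 28-day rule covers nearly all of the Week 8 to 12 window at Week 12, but only for the injected joints. Pain, both global assessments, HAQ-DI and CRP are not corrected. The plan itself makes such an injection an ACR20 failure despite the 28-day rule, and ACR50 and ACR70 have the same components.

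**3. The plan's own figure (Section 3.6.8)**

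Inputs: 66 per arm; ACR20 rates 25, 30, 45, 55 and 55%; Cochran-Armitage test, two-sided 0.05. Use equally spaced scores centred at zero, s = -2, -1, 0, 1, 2.

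- Mean: 66 × Σsp = 66 × 0.85 = 56.1
- Null SD: √(66 × 0.42 × 0.58 × 10) = √160.8 = 12.68
- Alternative SD: √(66 × Σs²p(1-p)) = √(66 × 2.1975) = 12.04
- Power: Φ[(56.1 - 1.96 × 12.68) / 12.04] = Φ(2.59) = 99.5%

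Simulation also gives 99.5%. With scores proportional to mg per 4 weeks and 15% dropout counted as non-response, power is 96.4%. The stated figure of more than 90% is confirmed, and it does not depend on the point raised here.

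**4. Possible size on a secondary responder endpoint (all inputs assumed)**

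Let f be the share of an arm with a failure event and an observed assessment, and q the share of those counted as responders. The arm's rate is overstated by f × q, and the active-minus-placebo difference changes by f₁q₁ - f₀q₀.

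Assume f₀ = 3 to 10% (placebo), f₁ = 1 to 3% (active) and q = 40 to 60%.

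- Placebo: 0.03 × 0.40 = 1.2 points to 0.10 × 0.60 = 6.0 points
- Active: 0.01 × 0.40 = 0.4 points to 0.03 × 0.60 = 1.8 points
- Change in difference, inputs varied independently: 1.8 - 1.2 = **+0.6** to 0.4 - 6.0 = **-5.6** points

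Pairing low with low and high with high gives -0.8 to -4.2 points, which hides the change of sign.

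For ACR50 a lower q is plausible. With q = 10 to 50% in all arms, the expected number of subjects in 330 who fail ACR20 in the primary analysis yet count as ACR50 responders at Week 12 is 66 × q × (f₀ + 4f₁):

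| f₀ | f₁ | Discordant subjects | Change in difference (points) |
|---|---|---|---|
| 2% | 2% | 0.7 to 3.3 | 0 |
| 5% | 2% | 0.9 to 4.3 | -0.3 to -1.5 |
| 10% | 5% | 2.0 to 9.9 | -0.5 to -2.5 |

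**The case against.** The strongest reply is that the plan already contains the damage. There is no in-study rescue arm: joint-count non-responders leave at Week 12, 16 or 20. Prohibited medication ends study drug, and the stable-MTX wording of the prohibited list arguably covers an MTX increase. Injected joints are penalised in all analyses. The secondary results are summaries with exploratory p-values, and Section 3.6.2 leaves detail to the SAP. Most of this stands, and it makes the effect small. It does not remove the three routes above, and nothing in the text reviewed here extends the failure rule.

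It can also be said that the Week 12 row of the ACR20-over-time table may simply reuse the primary variable. That is a fair reading, but it does not help ACR50 and ACR70, which have no failure rule under either reading.

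A reader might infer four stronger conclusions that the documents do not support:
- *That the effect of new medication is generally credited to secondary endpoints.* Discontinuation with non-responder imputation prevents this for most later binary outcomes.
- *That the bias favours placebo.* This requires failure events to be commoner on placebo. No rate is given, and Section 3.6.8 assumes dropout equally distributed between placebo and ALX-0061.
- *That LOCF carries Early Termination values to Week 24.* No text says so, although none excludes it.
- *That high-potency opioids are wrongly absent from the failure list.* Adding them would redefine the primary endpoint. That is a preference, not an inconsistency.

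**Conclusion.** The point holds as a gap in the scope of a stated rule. Followed as written, the plan allows an ACR20 non-responder in the primary analysis to be an ACR50 responder at the same visit, and it has no failure criterion for Weeks 12 to 24. This follows from the text and needs no assumed rate.

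The numerical effect is partial and unknown. The range of +0.6 to -5.6 points rests entirely on assumed event and response shares, and it includes zero. The trend test on Week 12 ACR20 and its power are unaffected. The change should be made for coherent tables and a clear meaning of response in the dose comparison, not because the main conclusion is at risk.

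**What to change.** In Section 3.6.4, and in the SAP before the Week 24 database lock:

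1. Apply the existing DMARD/biologic, MTX-increase and systemic corticosteroid criteria to every binary efficacy endpoint, at every visit from the date first met through Week 24.
2. Apply the Week 8 to 12 intra-articular criterion to all Week 12 binary endpoints, so that the Week 12 ACR20/50/70 rows agree with the primary analysis.
3. For continuous endpoints, state that values observed after a failure event do not feed LOCF.

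The cost is SAP wording and one derived flag from concomitant-medication data that the protocol already collects (Sections 3.3.6 and 3.4.1). Sample size, alpha and conduct do not change. Secondary response rates become slightly lower. Item 3 has a limit: the last value before failure may itself be a good one, so it removes the influence of the new medication but does not score the event as failure.

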### **3.6.4.2. SECONDARY EFFICACY ENDPOINTS**

For secondary efficacy endpoint evaluation summary statistics will be calculated as appropriate over time and by treatment group.

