## 2. OBJECTIVES

Primary objective:

- To assess the efficacy and safety of dose regimens of ALX-0061 administered s.c. in combination with MTX to subjects with active RA despite MTX therapy compared with placebo.

Secondary objective:

- To assess the effects of ALX-0061 on quality of life, PK, PD, and immunogenicity of ALX-0061, and to define the optimal dose regimen for ALX-0061, based on safety and efficacy, for further clinical development.

[figure not shown]

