Subjects will have visits at the site q2w up to and including Week 24 (or early termination). A Follow-up Visit will be planned 12 weeks after last study drug administration. Note that for subjects who withdrew for reasons of lost to follow-up, informed consent withdrawal, or death will not have any follow-up assessments.

The ACR20 response was chosen as the primary endpoint since this is a broadly accepted clinical response measure to demonstrate reduction in RA signs and symptoms and sensitive enough to differentiate from placebo effects. For details on primary statistical analysis in this study, please refer to section 3.6.4.1.

Note that higher levels of response, as measured by ACR50 and ACR70 response rates, and measures of remission using the DAS28, CDAI, SDAI, as well as the Boolean remission definition, will be used as supportive evidence of efficacy. In addition, endpoints, including ACR responses and disease activity scores, will be documented over time, including earlier time points, before the therapeutic plateau is expected. This will allow evaluation of potential differences in early clinical efficacy between the doses. Other RA domains, such as improvement in physical function and health-related quality of life, will be evaluated using the HAQ-DI, FACIT-Fatigue scale and the SF-36 questionnaires.

Safety and tolerability assessments will include evaluation of AEs (including serious adverse events, infections, injection site and hypersensitivity reactions), laboratory assessment, urinalysis, vital signs, and physical examination.

Additional planned assessments include the determination of ALX-0061 levels in serum, and PD biomarkers (including sIL-6R) in blood. To assess immunogenicity, the presence of ADA will be measured in serum until the Follow-up Visit, with potentially further characterization by modified ADA assay (mADA) and neutralizing antibody assay (nAb).

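### For the continuous secondary endpoints the protocol specifies no between-arm estimate and no baseline-adjusted model, although its aims include comparison with placebo and between doses

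*Combined protocol and SAP*

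**What the plan says.** Section 3.6.4.2 is a single sentence: "For secondary efficacy endpoint evaluation summary statistics will be calculated as appropriate over time and by treatment group". Section 3.6.4 lists the endpoints one by one. For DAS28, SDAI and CDAI, "The change from baseline (absolute change) in disease activity over time will be summarized by treatment group"; for physical function, "The change from baseline (absolute change) in HAQ-DI over time will be summarized by treatment group". SF-36 and FACIT-Fatigue are treated the same way at Weeks 12 and 24. The reported quantities are defined for each arm: "Summary statistics for continuous efficacy endpoints include mean (and associated 95% confidence interval), standard deviation, median, minimum and maximum". The synopsis gives the same kind of per-arm list.

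Not every continuous endpoint is on the change scale. ACR-N and the DAS28 score over time are summarised as such, and for stiffness the text reads "The duration of morning stiffness at Week 24 will be summarized by treatment group".

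One secondary endpoint is explicitly compared, and it is binary: "The proportion of subjects in remission over time will be summarized by treatment group and compared between the groups". No method is given for that comparison.

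The aims are wider than the analysis. Section 2 sets efficacy against placebo as the primary objective and, as a secondary objective, "to define the optimal dose regimen for ALX-0061, based on safety and efficacy, for further clinical development". Section 3.1.1, on ACR responses and disease activity scores recorded over time, says "This will allow evaluation of potential differences in early clinical efficacy between the doses".

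**The concern.** An interval for one arm's own mean change does not answer whether that arm differs from placebo or from the next regimen. Under the text as written, the report would show five means with five intervals for each scale, and readers would judge by eye how far they overlap. That is a poor guide to a difference. Chance differences between arms at baseline also feed into each arm's raw change.

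This matters because the primary analysis is not built to separate regimens. It is one trend test across five arms, and the supplementary ACR20 tests set each dose against placebo only. The sample size scenario assumes the same ACR20 rate, 55%, for 150 mg q2w and 225 mg q2w. If those regimens differ in efficacy, other endpoints have to show it, and the continuous scales are natural candidates. Section 3.1.1 says the regimens were chosen on predicted DAS28 response, yet no randomised between-arm estimate of DAS28 is specified.

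**Working it through.** **1. The plan's own figure.** The only power statement (section 3.6.8) is more than 90% for the Cochran-Armitage trend test, with ACR20 rates of 25/30/45/55/55%, 66 per arm and two-sided 0.05. Simulation of 200,000 trials gives:

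| Trend scores | No drop-out | 15% drop-out as non-responders |
|---|---|---|
| 0 to 4 | 99.5% | 97.7% |
| mg per 4 weeks (0, 75, 150, 300, 450) | 99.1% | 96.4% |

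The statement holds as a lower bound. The plan has no matching figure, and no SD or correlation, for any continuous endpoint.

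**2. Aims set against analyses.**

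| Stated aim | Specified for continuous endpoints |
|---|---|
| Efficacy against placebo (section 2) | Per-arm mean with its own 95% CI; no difference |
| Potential differences between doses (3.1.1) | Per-arm summaries over time; no difference |
| Optimal regimen (section 2) | Per-arm summaries; exposure-response model for DAS28 only (3.6.6) |

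**3. Precision formulae.** Let s be the baseline SD, k the ratio of follow-up to baseline SD, and r the correlation between baseline and follow-up. Per subject:

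- raw change: variance = s²(1 + k² − 2rk)
- ANCOVA on baseline: variance = s²k²(1 − r²)
- difference = s²(1 − rk)², so the relative reduction is (1 − rk)² / (1 + k² − 2rk)

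The numerator is a square, so under this common-variance model ANCOVA is never less precise, apart from the negligible cost of estimating one slope. With k = 1 the reduction simplifies to (1 − r)/2 and the variance ratio to (1 + r)/2.

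**4. Equal SDs (k = 1), 66 per arm.** The values of r are assumptions.

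| r | Variance ratio | Reduction | Raw-change n per arm for equal precision, 66/ratio | CI width ratio |
|---|---|---|---|---|
| 0.3 | 0.65 | 35% | 101.5 | 0.806 |
| 0.4 | 0.70 | 30% | 94.3 | 0.837 |
| 0.5 | 0.75 | 25% | 88.0 | 0.866 |
| 0.6 | 0.80 | 20% | 82.5 | 0.894 |

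**5. Unequal SDs, r from 0.3 to 0.6.** The values of k are also assumptions.

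| k | Reduction |
|---|---|
| 0.8 | 40-50% |
| 1.0 | 20-35% |
| 1.25 | 6-22% |
| 1.5 | 1-13% |

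The extremes: r = 0.3, k = 0.8 gives (1 − 0.24)²/(1 + 0.64 − 0.48) = 0.5776/1.16 = 0.498. For r = 0.6, k = 1.5 it is (1 − 0.90)²/(1 + 2.25 − 1.80) = 0.01/1.45 = 0.007.

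**6. Baseline imbalance.** If two arms differ by d at baseline, the expected difference in raw change moves by −(1 − rk)d. With 66 per arm one standard error of d is s√(2/66) = 0.174s. At k = 1 that moves the raw-change difference by 0.7 × 0.174s = 0.12s for r = 0.3, and by 0.4 × 0.174s = 0.07s for r = 0.6. ANCOVA removes this shift.

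**The case against.** A reader might infer that the plan has no analysis at all of dose differences on a continuous scale. The documents do not support that. Section 3.6.6 plans nonlinear mixed effects exposure-response modelling of DAS28 and ACR20, in a separate report, and that is a legitimate tool for dose selection. Section 3.6.2 leaves analysis details to an SAP to be finalised before the Week 24 database lock, so a model may be intended there. Both points narrow the gap without closing it. The model relates serum exposure to response, is not a randomised comparison of regimens, and omits SDAI, CDAI, HAQ-DI, SF-36 and FACIT-Fatigue. The deferral supplies no analysis in the file.

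A reader might also take section 3.1.1 as promising a formal comparison. It says only that the data will allow potential differences to be evaluated, which per-arm results partly serve.

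Mean change, SD and n by arm let a reader work out an unadjusted difference and its interval. That stands. The adjusted difference can be approximated only where baseline, visit and change summaries are all tabulated, which the endpoint list provides for DAS28 but not for the other scales.

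Finally, descriptive secondary reporting is a recognisable Phase IIb choice, and the plan calls all p-values outside the primary trend test exploratory. That also stands. It argues for labelling the estimates exploratory, not for leaving them out.

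**Conclusion.** The point holds as a limited, low-cost improvement that should be made. The protocol text specifies neither a randomised between-arm estimate nor a baseline-adjusted model for the continuous secondary endpoints, while its aims call for comparison with placebo and between regimens. The sample size, the primary test and trial conduct are untouched.

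The direction of the precision gain is secure; its size is not. It would be tempting to say that the plan gives away 20-35% of the variance. That needs r of 0.3 to 0.6 and equal SDs, neither of which is in the documents, and it concerns a contrast that the plan does not define. Letting the SD ratio run from 0.8 to 1.5 widens the range to about 1-50%. Entry requires at least 6 swollen and 6 tender joints, and CRP above the upper limit of normal at screening. This truncates baseline activity, so a follow-up SD above the baseline SD, and hence a smaller gain, is plausible for joint-based scores. The case rests mainly on the missing contrast; precision is a bonus.

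Nor can it be said that these endpoints are all reported only as raw change, since ACR-N, the DAS28 score and morning stiffness are not.

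**What to change.** In section 3.6.4.2 or in the SAP, before the Week 24 database lock:

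- For each of DAS28, SDAI, CDAI, HAQ-DI, SF-36 and FACIT-Fatigue at Week 12, fit an ANCOVA with treatment (five levels) and the baseline value of that endpoint. Region is an optional covariate; section 3.3.8 describes no stratification that would require it.
- Report adjusted mean differences with 95% CI for each regimen against placebo and for the adjacent pairs: 75 mg q4w and 150 mg q4w, 150 mg q4w and 150 mg q2w, 150 mg q2w and 225 mg q2w. Label them exploratory.
- Keep the descriptive tables.
- Flag any Week 24 contrast as resting on last observation carried forward after the efficacy discontinuations at Weeks 12, 16 and 20. A narrower interval there could suggest more certainty than the data hold. Week 12 is cleaner, because the Week 12 visit is itself the Early Termination Visit for subjects who meet the rule then.

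The baseline values are already needed for the planned change scores, so no new data are required. The cost is SAP wording and a few extra exploratory tables. The primary test does not change.
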